1.2 Stage 1 summary

The primary objective of Stage 1 was to assess the safety and tolerability of CBZ in the treatment of children with MCDS who are ambulant but have not yet reached skeletal maturity (open epiphyses) and to determine an appropriate dose of CBZ to inform the treatment of children in Stage 2.

A cohort of eleven patients were evaluated through a review of safety and tolerability. Data presented to the DMC included the number and reason for any DLTs, laboratory safety assessments, abnormal physical examinations, pain scores and adverse events. Initially, the Stage 1 safety review [report dated 9/8/2021] was presented to the IDMC when six patients in Stage 1 reached their maximum tolerated dose or 20mg/kg. A subsequent report was presented to the DMC [25/10/2021] once the last patient on CBZ in Stage 1 reached the 6-month time point.

Following these reviews, the IDMC recommended continuation of the trial according to the current version of the protocol (Version 6.0 dated 30 June 2021) with no changes and agreed that the IMP dose regimen to be implemented in Stage 2 of the study should be 20 mg/kg.

1.3 Stage 2 Objectives

1.3.1 Primary objective

To evaluate efficacy of CBZ for the treatment of children with MCDS who are ambulant but have not yet reached skeletal maturity (open epiphyses) and to determine if the level of efficacy warrants a subsequent formal development programme for CBZ in this indication.

1.3.2 Secondary objectives

To evaluate the effect of CBZ on height, bone conformation, pain, and health related quality of life in children with MCDS over 12 months.

2 Study Methods

2.1 Study setting and patient population

Stage 1 of MCDS-Therapy was conducted at two centres within the UK: The Newcastle upon Tyne Hospitals NHS Foundation Trust Newcastle upon Tyne UK (NuTH) and Guys and St. Thomas' Hospital London UK (GSTFT).

Stage 2 includes sites across the UK, and self-sponsored trial sites across Europe and Australia.

The following sites were expected to recruit to Stage 2:

- I. The Newcastle upon Tyne Hospitals NHS Foundation Trust, Newcastle upon Tyne UK (NuTH)
- II. Guy's and St. Thomas' Hospital, London UK (GSTFT)
- III. Rizzoli Orthopaedic Institute, Bologna Italy (IOR)
- IV. University of Freiburg- Freiburg Germany (UKL-FR)
- V. Assistance Publique Hôpitaux de Paris Paris France (AP-HP)
- VI. Murdoch Children Research Institute, Melbourne Australia (MCRI)
- VII. University of Antwerp, Antwerp Belgium (UZA)

As the dosing regimen for Stage 2 remains the same as for Stage 1 (20 mg/kg), Stage 1 participants will be included in Stage 2 analysis.

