Summary of Trial Design	A two-stage open-label, single arm phase I/IIa trial of carbamazepine in children with skeletal dysplasia who are outpatients. The trial includes an initial dose determination stage (Stage 1) followed by long-term assessment of efficacy and safety at the chosen dose (Stage 2).			
Summary of Participant Population	Children with a diagnosis of Metaphyseal chondrodysplasia, type Schmid (MCDS) with confirmed COL10A1 pathogenic mutation.			
Planned Sample Size	40 participants (11 participants Stage 1 dose titration; 29 participants Stage 2 treatment)			
Baseline Observation Duration	Stage 1 participants: 12-18 months (dependent on covid-19 impact)Stage 2 participants : 6 months			
Treatment Duration	Stage 1 participants: 24 months + additional optional 12 months*			
	Stage 2 participants: 12 months*			
	*LPLV must occur no later than 31 st January 2024			
Planned Trial Period	70 months			
	Objectives	Outcome Measures		
STAGE 1 – DOSE TITRATIO	N & TOLERABILITY			
Primary	To assess the safety and tolerability of carbamazepine (CBZ) in the treatment of children with MCDS who are ambulant but have not yet reached skeletal maturity (open epiphyses)	Laboratory safety assessments, adverse events and physical examinations collected post IMP administration.		
	To determine an appropriate dose of CBZ to inform the treatment of children with metaphyseal chondrodysplasia, type Schmid in Stage 2.	Outcome of dose-titration safety review at 6 months post IMP treatment initiation.		
Secondary	To evaluate the effect of CBZ on pain in children with MCDS over 24 months	 Alteration from baseline in pain perception over 24 months as measured by: PEDSQL Pain Coping Inventory PEDSQL Pain Questionnaire 		

STAGE 2 – TREATMENT			
Primary	To evaluate efficacy of CBZ for the treatment of children with MCDS who are ambulant but have not yet reached skeletal maturity (open epiphyses)	Alteration from baseline in growth velocity over 12 months	
	To determine if efficacy of CBZ warrants a subsequent formal development programme for carbamazepine in this indication	Growth velocity follow-up data at 12 months post treatment initiation	
Secondary	To evaluate the effect of CBZ on height in children with MCDS over 12 months	Alteration from baseline in height percentile over 12months	

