8.8.7 Continuation of treatment with CBZ for Stage 1 participants

Assuming Stage 1 participants have achieved their MTD and no significant safety concerns arise from the dose titration 6 month safety review, participants from Stage 1 will continue treatment with CBZ. They will receive the dose approved by the trial IDMC until they have received 24 months of IMP treatment (post initiation of IMP treatment) to allow their data to be included in the Stage 2 final analysis. If a participant has not reached the dose approved by the trial IDMC, they will continue on the maximum dose they were able to tolerate until they have received 24 months of IMP. Stage 1 participants will continue to attend trial visits every three months as indicated in the schedule of events –treatment (Table 7) and the participant visit schedule (Table 4). Eligible Stage 1 participants in the UK, who commenced treatment before 2nd March 2021, will have the option to continue treatment with CBZ for an additional 12 months after they have completed 24 months of IMP treatment. All trial visits must be completed by 31st January 2024.

Assuming the dose regimen is sufficiently similar in stage 1 and 2, stage 1 patients will be included in the analysis at the end of the trial, using the primary endpoint measured at the end of the dose titration phase for stage 1 and at the end of 12 months of treatment for stage 2. If the dose regimen changes between stage 1 and stage 2, we will consult with the IDMC as to whether stage 1 and stage 2 patients should be combined in the final analysis.

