2.7 Overview of MCDS-Therapy Clinical Trial (from Protocol)

*The 12 month baseline observational visit may be rescheduled to a 18 month visit for participants who have missed the 12 month visit due to COVID-19 (Stage 1 UK participants only).

[^] To aid with study participant retention due to COVID 19, with discussion with the CI, the 12 month baseline observational visit window can be up to 12 months and 8 weeks. This will be assessed on a case by case basis through discussion with the site PI^a with approval from the CI and the NCTU team notified.

Eligible Stage 1 participants may continue treatment for further 12 months (up to 36 months) subject to a separate informed consent at visit 2.5.

Last Patient Last Visits in Stage 1 and Stage 2 must be completed by 31st January 2024.

3 Study Population

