4.2 Analysis populations

There will be two analysis populations:

1. Participants who have completed the baseline observation period and have received at least one dose of CBZ.

2. Participants who have completed their baseline observation period and have been prescribed, on average, at least 15 mg/kg of CBZ over their first 12 -months of treatment, i.e. a dose which is at least 75% of the dose recommended from Stage 1. Note that some participants will have longer than 12 months of treatment.

Adverse events will be reported for all participants who start their baseline period.

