5.1.1 Adverse events

The number of adverse events and adverse reactions (those possibly, probably or definitely related to treatment) and the worst grade AE and AR per participant will be summarised descriptively.

Example table: Number of events per participant

	Mean (SD)	Median (Q1, Q3)	Min, Max
All adverse events			
Adverse reactions (possibly, probably, definitely)			

Example table: Worst grade reported per participant (number, %)

	None	Mild	Moderate	Severe
All adverse events				
Adverse reactions (possibly, probably, definitely)				

The number of participants reporting each type of adverse event (by MedDRA System Organ Class) will be tabulated.

Example table: Number and percentage of participants affected by each adverse event, reported by System Organ Class

Event term		Total		Mild		Moderate		Severe	
	Ν	%	Ν	%	Ν	%	Ν	%	
Blood and lymphatic system disorders									
Cardiac disorders									
Endocrine disorders									
Eye disorders									
Gastrointestinal disorders									
General disorders and administration site conditions									
Immune system disorders									
Infections and infestations									
Injury, poisoning and procedural complications									
Investigations									
Metabolism and nutrition disorders									

The number and percentage of patients experiencing at least one high grade event (grade 3/4/5).

A line listing of all AEs will be reported, by participant, including severity, seriousness and relationship to study treatment.

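### Adverse events are tabulated per child over 12 months on drug for some children and 24 to 36 for others, so the pooled figures describe no defined period

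*SAP*

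**What the plan says.** The protocol summary plans "40 participants (11 participants Stage 1 dose titration; 29 participants Stage 2 treatment"). It gives treatment duration as "Stage 1 participants: 24 months + additional optional 12 months" and "Stage 2 participants: 12 months". SAP 2.7 repeats the extension: "Eligible Stage 1 participants may continue treatment for further 12 months (up to 36 months"). Protocol 8.8.7 limits that option to eligible UK Stage 1 children "who commenced treatment before 2nd March 2021, will have the option to continue treatment with CBZ for an additional 12 months", and requires every visit to be finished by 31 January 2024.

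SAP 2.1 brings Stage 1 into the Stage 2 analysis because the dosing "remains the same as for Stage 1 (20 mg/kg), Stage 1 participants will be included in Stage 2 analysis". That sentence does not mention safety. The safety population comes from SAP 4.2: "Adverse events will be reported for all participants who start their baseline period". SAP 5.1.1 then sets the summaries: the number of events and reactions per child, with "the worst grade AE and AR per participant will be summarised descriptively". It adds the number and percentage of children affected by organ class, and the number and percentage with any grade 3 to 5 event. The example tables have no column for stage or study period. The adverse-event line listing is described by severity, seriousness and relationship to treatment. Onset date appears only in the serious-event listing of SAP 5.1.2.

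**The concern.** A cumulative count, or a proportion with at least one event, means something only together with the time over which it accrued. Here that time is at least twice as long in Stage 1 as in Stage 2. Giving both stages the same dose does not give them the same exposure. The pooled mean and percentages would be neither 12-month nor 24-month figures, and they would move with the number of families who took up the extension.

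At stake is how the harms are read beside the benefit. The Stage 2 outcomes are worded over 12 months, and SAP 1.3.1 uses the results to judge whether a formal development programme is warranted. A reader weighing a 12-month growth effect against these tables would have no 12-month toxicity figure. The listing as specified would not let them rebuild one for non-serious events.

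**Working it through.** The documents state no adverse-event rate, so there is no planned figure to reproduce. The inputs are the planned numbers and durations above; the event rates are assumptions.

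**1. Planned on-drug time**

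- Stage 2: 29 × 12 = 348 child-months.
- Stage 1, no extension: 11 × 24 = 264. Total 612, mean 612/40 = 15.3 months (1.275 years). Stage 1 share 264/612 = 43%.
- Stage 1, all 11 to 36 months: 11 × 36 = 396. Total 744, mean 744/40 = 18.6 months (1.55 years). Stage 1 share 396/744 = 53%.

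Stage 1 is 11/40 = 27.5% of the children. With a constant event rate, mean events per child are 1.275 times the 12-month figure, with a ceiling of 1.55 times.

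**2. Whether the ceiling is reachable**

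A child must have started by 31 January 2021 to complete 36 months by 31 January 2024. The option is open to starts before 2 March 2021. The number of starts on either side of these dates, and the number who consented to extend, are not given. The extension count is therefore somewhere between 0 and 11.

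**3. Percentage with at least one event, constant rate r per year**

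First 12 months: 1 − e^(−r). Pooled: [29(1 − e^(−r)) + 11(1 − e^(−kr))]/40, with k = 2 (no extension) or k = 3 (all extend).

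For r = 0.3 and k = 2: (29 × 0.2592 + 11 × 0.4512)/40 = 12.48/40 = 0.312. For k = 3: (29 × 0.2592 + 11 × 0.5934)/40 = 14.04/40 = 0.351.

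| Assumed r | First 12 months | Pooled, k = 2 | Pooled, k = 3 (ceiling) |
|---|---|---|---|
| 0.1 | 9.5% | 11.9% | 14.0% |
| 0.3 | 25.9% | 31.2% | 35.1% |
| 1.0 | 63.2% | 69.6% | 72.0% |

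**4. Early-onset case**

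If all reactions fall in titration, extra months add nothing and the pooled percentage equals the 12-month percentage.

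**5. Direction**

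For a fixed set of treated children, adding later on-drug time can raise a cumulative count or percentage or leave it unchanged; it cannot lower it. This needs no assumption about the hazard.

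**6. Pre-drug time**

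SAP section 5 records events from consent, and SAP 2.4.1.1 gives 12 to 18 months of observation before drug in Stage 1 against 6 in Stage 2. Untreated time is (11 × 12 + 29 × 6)/(11 × 48 + 29 × 18) = 306/1050 = 29% of planned follow-up at the low end. At the high end it is (11 × 18 + 29 × 6)/(11 × 42 + 29 × 18) = 372/984 = 38%. The all-events rows mix this with on-drug time. The reaction rows largely avoid it, but they do not equalise on-drug time.

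**7. Detection in the first 12 months**

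Protocol Table 6 schedules Stage 1 a week-2 visit and on-drug laboratory tests at week 2 and months 3, 6, 9 and 12. Table 9 schedules Stage 2 tests on drug at months 6 and 12.

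**The case against.** **The absolute shift is modest.** At r = 0.3 it is 12.5 children against 10.4 (40 × 0.259), so about 2 of 40, and about 4 at the ceiling. The 95% half-width around 26% with 40 children is 1.96 × √(0.26 × 0.74/40) = 14 points, and no decision threshold hangs on these tables. That stands as a limit on importance. It does not supply the missing time base.

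**Full-follow-up safety reporting matches the efficacy analysis.** The growth model in SAP 4.3.1 has no 12-month cut, and SAP 4.3.4 keeps growth data from extended treatment. But the growth parameter is a change in slope, already expressed per unit time, so longer follow-up does not mechanically enlarge it as it does a cumulative count. The protocol also uses a common window elsewhere: Protocol 8.8.7 takes the primary endpoint at the end of the 12-month titration phase for Stage 1 and at 12 months for Stage 2.

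**Part is covered elsewhere.** Protocol 8.8.6 sends a 12-month Stage 1 safety analysis to the IDMC, serious events are listed with onset dates, and the table shells are only examples. This helps the IDMC and covers serious events. It does not put a defined period on the final tables.

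**Two stronger readings are not supported.** A reader might infer that Stage 1 families were questioned more often because of the weekly calls. SAP 3.1.6 gives Stage 2 weekly calls until a stable dose, Protocol Table 9 records adverse events at them, and the Stage 1 calls are also made only as required. A reader might also take the SAP 2.1 sentence as itself pooling the safety data. It does so only when read with SAP 4.2 and 5.1.1.

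**Conclusion.** The point holds and should be addressed. Followed as written, SAP 5.1.1 gives per-child counts and crude percentages that correspond to no defined period on CBZ. The direction is certain for the same treated children; the size is not. On planned durations, mean on-drug time is 1.28 years without extension, with 1.55 as an upper limit. At an assumed constant 0.3 per year, the percentage with an event is 31% (ceiling 35%) instead of 26%.

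It would go too far to say that the tables will overstate 12-month toxicity by 27% to 55%. Those figures apply to mean counts under a constant rate, and the upper one needs all 11 Stage 1 children to complete 36 months. If reactions cluster in the weekly dose escalation, the excess is small. Withdrawals and visits brought forward to 31 January 2024 would also change the figures. Children who start baseline but never take drug would dilute the percentages. None of these numbers is given. The growth analysis is not affected.

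**What to change.** In SAP 5.1.1:

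- Make the main on-treatment adverse-event and adverse-reaction tables cover the first 12 months after the first CBZ dose, in treated children only, with Stage 1, Stage 2 and total columns. State how many children completed the window, since some final visits may be brought forward.
- Add events per person-year on CBZ over full exposure, by stage and in total. On planned durations the denominator is 51 to 62 child-years (612/12 to 744/12).
- Show Stage 1 events after month 12 and pre-drug events in separate columns or tables.
- Add stage, study period and onset date to the adverse-event line listing.
- Note beside the stage comparison that Stage 1 had the week-2 visit and more scheduled laboratory tests in its first 12 months.

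The cost is SAP wording and a wider set of tables, with smaller headline counts because later events move elsewhere. No trial procedure changes. The change relies on onset dates for non-serious events, which the documents state explicitly only for serious ones. Surgical interventions, recorded on the adverse-event form (SAP 2.5), are to be reported by three-month period (SAP 4.4.3), which suggests that event timing is held, but this should be confirmed.

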2.2 Eligibility criteria

For a full list of inclusion and exclusion criteria see the protocol, version 9.0 (16th October 2023).

2.2.1 Inclusion criteria

Participants will be those with a proven diagnosis of MCDS; a pathogenic mutation in the gene encoding the Collagen Type X Alpha 1 Chain - Schmid Metaphyseal Chondrodysplasia (COL10A1) protein and ambulant at the time of consent/assent, with open epiphyses. Female patients of childbearing potential must have a negative pregnancy test at baseline and agree to regular pregnancy testing during the trial; sexually active female patients of childbearing potential are required to practice true abstinence.

2.2.2 Exclusion criteria

Patients will be excluded if they: have reached skeletal maturity; are known to have atrioventricular block; have had a prior adverse reaction to CBZ or a similar drug; have a history of bone marrow suppression/depression; have evidence of chronic hepatic or renal impairment; have acute intermittent porphyria; have received a monoamine oxidase inhibitor within 14 days of commencing therapy; or have abnormal blood screening results at the time of treatment initiation. Patients of Han Chinese, Thai and

other Asian origins who carry the HLA-B*1502 allele are excluded, as are patients who have a planned surgery or planned osteotomy.

2.3 Randomisation and blinding

There is no randomisation or blinding in this trial.

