8.7.8 X-ray analysis & Bone alignment

Participants will have an X-ray of the hips/knees and left wrist during baseline observation (post confirmation of eligibility), stage 1 dose titration and tolerability (every 6-12 months) and stage 2 treatment (every 6-12 months), as specified in the schedule of events (Tables 5, 6, 7, 8 & 9). A maximum of 20 sets of X-rays will be conducted over a 48 month period. Participants will receive up to two wrist and two hip/knees X-rays during baseline observation period and up to six wrist and six hip/knees X-rays during the 12-24 month dose titration/treatment period. Participants who consent to additional visits in the optional Extended Treatment Phase would receive two additional wrist and two additional sets of hip/knee X-rays.

Imaging to be collected: -

- Long leg standing Anterior-Posterior (AP) views (hips & knees)
- Left wrist (to assess bone age)

Both entire lower extremities (including a full view of the anterior superior iliac crest and the ankle talus) will be imaged at the same time, in a weight-bearing position.

Anonymised X-ray images will be stored in the trial MACRO database, labelled with unique study ID only. X-ray images will be reviewed by at least two independent radiologists to ensure consistency across sites has been achieved.

Using X-ray images of the hip and knees, bone alignment will be evaluated based on the angle formed between the head and neck of the femur and its shaft (Mikulicz angle). To ensure consistency, angle measurements will be performed centrally by at least two independent radiologists . This will be

measured according to the standards described in Keats TE Atlas of Roentenographic measurement Mosby 1990 p.289 p.320.

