2.4.1.2.1 Alteration from baseline in height percentile over 12 months

Total height (length if age <2 years); sitting height (age \ge 5 years) and crown-rump length (age <5 years) are recorded at each baseline and treatment visit.

Height for age and sex, *zscores* are calculated using the ZANTHRO function in STATA; the "British 1990 Growth Reference" charts are used as the standard.

Vidmar, S. I., Cole, T. J., & Pan, H. (2013). Standardizing Anthropometric Measures in Children and Adolescents with Functions for Egen: Update. The Stata Journal, 13(2), 366–378. https://doi.org/10.1177/1536867X1301300211

2.4.1.2.2 Alteration from baseline in long bone alignment and configuration over 12 months as measured by X-ray analysis.

Using X-ray images of the hip and knees, bone alignment will be evaluated based on the angle formed between the head and neck of the femur and its shaft (Mikulicz angle), the femoral neck-shaft angle (NSA). To ensure consistency, the NSA will be assessed centrally by at least two independent radiologists to ensure consistency across sites. This will be measured according to the standards described in Keats TE Atlas of Roentenographic measurement Mosby 1990 p.289 p.320.

Outcome measures are:

- A. Bone age SD age related zscore (taken from the left wrist x-ray)
- B. Tanner and Whitehouse bone age (TW3)??
- C. Femoral neck-shaft angle (NSA) on left and right legs
- D. Deviation from midline at knee

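### Neither document masks the X-ray readers to film date or treatment period, so a reading shift on on-treatment films would enter the plotted before-after changes

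*SAP*

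**What the plan says.** The protocol summary describes "A two-stage open-label, single arm phase I/IIa trial of carbamazepine in children with skeletal dysplasia". SAP 2.3 is one sentence: "There is no randomisation or blinding in this trial". It does not separate families, clinicians and image readers.

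Protocol 8.7.8 covers the films. On storage: "Anonymised X-ray images will be stored in the trial MACRO database, labelled with unique study ID only". On review: "X-ray images will be reviewed by at least two independent radiologists to ensure consistency across sites has been achieved". On measurement: "angle measurements will be performed centrally by at least two independent radiologists". SAP 2.4.1.2.2 repeats the last point for the hip: "the NSA will be assessed centrally by at least two independent radiologists to ensure consistency across sites". The only purpose given for using two readers is consistency.

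SAP 2.4.1.2.2 lists the radiographic outcomes: a bone-age z-score from the left wrist film, TW3 bone age (still marked with question marks), the femoral neck-shaft angle on each leg, and "Deviation from midline at knee". For bone age and knee deviation neither document states central reading. Only the general review of images by at least two radiologists applies to them.

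SAP 4.4.1 has these outcomes plotted by child, with baseline and treatment visits marked. SAP 4.4.2 names the outcomes that enter the GEE model (height z-score, pain scores and PedsQL scores) and includes no radiographic outcome.

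**The concern.** An open-label trial cannot hide treatment from families or clinicians, but it can hide film date and treatment period from the people who measure the films. The plan does not do so. A label that carries only the study ID conceals the child's name. It does not conceal whether a film was taken before or during carbamazepine, and that contrast is the treatment comparison.

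Neck-shaft angle, knee deviation and bone age all call for some reader judgement. If readers who know the period measure later films slightly more favourably, the result looks like a drug effect, and there is no control group in which the same shift would show.

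Bone alignment matters to the trial's conclusion. Protocol section 3 and SAP 1.1 name it, with growth velocity, quality of life and pain, as a basis for judging efficacy. Protocol 2.3 ties it to whether a randomised trial should follow. It is also one of the few outcomes here that could be protected from open-label expectation.

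**Working it through.** The plan has no figure to reproduce. The sample size of 40 was set by feasibility (SAP 2.6), and no SD, effect size or reader error is given for any X-ray outcome. The check is a comparison of passages and a short piece of algebra.

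**1. What the documents provide**

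- Identity of the child: hidden (protocol 8.7.8).
- Film date and visit: no provision for hiding them.
- Treatment period: no provision for hiding it; SAP 2.3 states there is no blinding and makes no exception.
- Reading order and access to earlier readings: not mentioned.
- Purpose of two readers: consistency only (protocol 8.7.8, SAP 2.4.1.2.2).

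**2. Does film order reveal period?** Yes. For a Stage 2 child, protocol Tables 8 and 9 schedule films at baseline visit 1, then at visits 2.1, 2.3 and 2.5. The first two are taken before or at the start of treatment, the last two at 6 and 12 months on drug. For a Stage 1 child (Tables 5 to 7), films at visits 1, 3 and 1.1 are taken before or at the start, and every film from visit 1.4 onwards is on drug. A reader who knows the order therefore knows the exposure.

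**3. Where a reading shift goes.** Let *a* be the true value, *e* random reading error, and δ a systematic shift applied to on-treatment films.

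- Baseline reading: y₀ = a₀ + e₀
- On-treatment reading: y₁ = a₁ + δ + e₁
- Change: y₁ − y₀ = (a₁ − a₀) + δ + (e₁ − e₀)

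Averaged over *n* children, the expected change is the true mean change plus δ. The random part shrinks as *n* grows, but δ does not depend on *n*.

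**4. Does a second reader help?** If readers A and B are averaged, the bias is (δ_A + δ_B)/2. With a shared expectation, δ_A = δ_B = δ, and the average is still δ. The systematic difference between them, δ_A − δ_B, is then 0, so good agreement would not reveal the problem.

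**5. What it would affect.** Under SAP 4.4.1, δ would displace every on-treatment point in the individual plots of neck-shaft angle, knee deviation and bone age. Under SAP 4.4.2 no radiographic outcome is modelled, so no confidence interval or test result carries it. The primary outcome (SAP 4.3) uses height and does not involve the films.

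**The case against.** **Silence is not evidence of unmasked reading.** SAP 2.3 is a general line about an open-label design. A reader might infer from it that the radiologists do read each child's films in sequence, knowing which are on drug. The documents do not say so. They do not describe what readers see, and protocol 13.3 describes role-based database access for site staff and the trials unit without mentioning radiologists. This stands: what can be shown is a missing safeguard, not a bias that has occurred.

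**No planned test is inflated.** A reader might also attach an error rate. With a paired t-test at two-sided 5% and assumed shifts of 0.1, 0.2, 0.3 and 0.5 SD of within-child change, the false-positive rate would be 9.5%, 23.5%, 45.7% and 86.9% with 40 children, or 8.2%, 18.0%, 34.5% and 73.9% with 29. But the shifts are assumptions, the documents give no SD, and the SAP plans no such test. These rates apply to nothing in the plan.

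**Scope.** It would be too much to say that central readers measure all three outcomes. Central reading is stated only for angle measurements and the neck-shaft angle.

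**Limited benefit and some cost.** Growth can reveal the order of a child's films, so masking is partial. Nor does it solve the larger difficulty of an uncontrolled comparison in growing children, namely change with age or disease course. And it is not free: SAP version 1.0 is dated 08/02/2024, and the protocol's amendment history puts the final report at 31 May 2024, which leaves 21 + 31 + 30 + 31 = 113 days, about 16 weeks.

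These points limit the size of the concern. None supplies the missing safeguard.

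**Conclusion.** The point holds in limited form. SAP 2.3 disclaims blinding, and no passage masks the X-ray readers to date, visit or treatment period. Labelling by study ID hides identity only, and using two readers addresses consistency only. If readers know the period and shift their on-treatment readings, the shift enters the change in neck-shaft angle, knee deviation and bone age in full.

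No number can be put on the shift from the documents. Whether one arises depends on two things they do not settle: what readers see, and whether that influences them. The consequence would be a biased plot or description of secondary outcomes. It would not be a false-positive test result or a threat to the height-based primary outcome. Since bone alignment is named as a basis for judging efficacy, and the same readers can be masked at low cost, the change is worth making.

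**What to change.** Amend SAP 2.3, SAP 2.4.1.2.2 and protocol 8.7.8 to state that:

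- the existing radiologists read neck-shaft angle, knee deviation and bone age from films with date, visit and treatment period removed;
- films are presented in random order across children and visits;
- readers have no access to earlier readings or chronological age;
- the statistician re-links age and date after reading and only then derives the bone-age z-score;
- films already read unmasked are re-read where feasible, and otherwise reported as unmasked.

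The cost is relabelling, batch reading late in the trial and possibly some repeat readings. As a rough count, assuming full enrolment, no missed films and coinciding visits combined, Stage 2 gives 29 × 4 = 116 film sets and Stage 1 gives 11 × 6 = 66. That is 182 in all, or up to 182 + 11 × 2 = 204 if every Stage 1 child took the optional extension. The last permitted visit (31 January 2024) precedes the SAP date, so batch reading need not wait for further films. Because growth may still reveal order, the report should describe the masking as partial.
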